2.1 Primary objective

To document the long-term safety and tolerability profile of pasireotide s.c. when administered as monotherapy or in combination with other therapies in patients with Cushing's disease.

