3.4.1.1 Treatment discontinuation

Patients who permanently discontinue treatment with pasireotide s.c. prior to the 3-year observation period will have to be withdrawn from this study. Patients who discontinue pasireotide s.c. treatment because of an adverse event, must be followed by the investigator until resolution of the AE or until 3 months following discontinuation of drug whichever is longer.

All available safety and efficacy parameters will be collected for a period of 3 months following the last dose of pasireotide s.c. for patients who permanently discontinue pasireotide s.c. prior to completing the 3-year observation period.

Patients may voluntarily withdraw from this study or discontinued at the discretion of the investigator at any time. If such withdrawal occurs the investigator should determine the primary reason for a patient's premature withdrawal from this study. The withdrawal reason should be categorized into one of the following:

- Adverse event(s)
- Protocol deviation
- Subject withdrew consent or equivalent document (e.g., written information) as per country regulation
- Lost to follow-up
- Administrative problems
- Death
- Unsatisfactory therapeutic effect

For patients who are lost to follow-up, the investigator should show "due diligence", for the first 3 months after the last known date the patient took pasireotide, by documenting in the source documents steps taken to contact the patient, e.g. evidence of two certified letters, dates of telephone calls, sent emails.

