
Reports of lack of efficacy without an associated clinical event must be recorded on the AE CRF even if lack of efficacy parameters are being collected and recorded elsewhere within the study database.

- Overdose
- Intentional drug abuse and misuse
- Medication errors including drug maladministration
- Dispensing or prescribing errors

Reports of overdose, drug abuse and misuse, drug maladministration and dispensing errors/medication errors without an associated clinical event must be recorded on the AE CRF irrespective of whether or not the information is also being captured on the drug administration record form.

- Drug dependence or addiction
- Withdrawal reaction/syndrome or rebound symptoms
- Unexpected beneficial effect
- Treatment non-compliance (with clinical symptoms)

Note: Occupational or accidental exposure, for example of study personnel or family members of the patient should be reported to the local Health Authority in accordance with national regulatory requirements for individual case safety reporting or Recordati as a spontaneous report.

Any treatment of any adverse event should be recorded on the Adverse Event CRF. Some examples of treatment to be recorded are: no action taken (i.e., further observation only); drug of interest dosage adjusted/temporarily interrupted; drug of interest permanently discontinued due to this adverse event; treatment medication introduced or adjusted; non-drug therapy given; patient hospitalized/patient's hospitalization prolonged.

Once an adverse event is detected, it should be followed until its resolution or until it is judged to be permanent, and assessment should be made at each visit (or more frequently, if necessary) of any changes in severity, the suspected relationship to the drug of interest, the interventions required to treat it, and the outcome.

Information about common adverse effects already known about the medicinal product can be found in the locally available labeling document for the approved indication under evaluation in this study.

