6.7 Sample size and power considerations

The sample size for this study is not based on statistical considerations. It is anticipated that up to approximately 100 sites in about 35 countries will participate in the study. The study will enroll a minimum of 100 patients up to a maximum of 200 patients. The actual sample size may differ from this planned number.

7 Procedures and instructions

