## Tables

- Patient disposition (FAS)
- Analysis set
- Demographics and baseline data (FAS)
- Relevant medical history and current medical conditions by primary system organ class and preferred terms (Safety Set)
- Duration of exposure to study drug (Safety Set)
- Shift tables of biochemistry and hematology using CTC grades from baseline to the worst post-baseline value (Safety Set)
- Adverse events regardless of relationship with pasireotide s.c. by primary system organ class, preferred term (Safety Set)
- Adverse events regardless of relationship with pasireotide s.c. by preferred term (Safety Set)
- Adverse events regardless of relationship with pasireotide s.c. by primary system organ class, preferred term, maximum severity (Safety Set)
- Deaths by primary system organ class, preferred term (Safety Set)
- Serious adverse events regardless of relationship with pasireotide s.c. by primary system organ class, preferred term (Safety Set)
- Adverse events leading to study drug discontinuation, regardless of relationship with pasireotide s.c. by primary system organ class, preferred term (Safety Set)
- Adverse events with suspected relationship to pasireotide s.c. by primary system organ class, preferred term (Safety Set)
- Findings of the gallbladder imaging (presence of gallstones, presence of sludge, dilatation of ductal system, thickening)

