### 8.4.1 Adverse events (AEs)

All adverse events and the cause of death, as recorded on the completion CRF pages, will be coded using the latest version of the MedDRA coding dictionary that provides the system organ class (SOC) and preferred term (PT) information.

The number and percentage of patients reporting any AE will be summarized by primary SOC and PT. AEs and Serious Adverse Events (SAEs) will be reported and collected from patient's enrollment into the study until 28 days after the last dose of pasireotide s.c. at the patient's last follow-up visit. AEs and SAEs will be collected until 90 days after the last dose for patients who permanently discontinue pasireotide s.c. prior to completing 3 years of treatment.

The primary endpoint of this study is the percentage of patients having any pasireotide s.c.- related AEs and SAEs during the 3-year observation period. Pasireotide s.c.-related AEs are AEs for which the investigator suspected a relationship with pasireotide s.c.

AEs that started or worsened during the on-treatment period are called treatment-emergent AEs.

The incidence of treatment-emergent AEs will be summarized by system organ class (SOC), preferred term (PT) and severity. A patient with multiple occurrences of an AE will be counted only once in the respective AE category.

---

Study Code: CSOM230B2410

The following selection of treatment-emergent AEs will be listed and summarized, overall and by cohort:

- AEs regardless of relationship with pasireotide s.c. (additionally by country). This summary (> 5% in all patients) will also be prepared for the subgroup of patients from German sites
- AEs suspected to be related to pasireotide s.c.
- SAEs regardless of relationship with pasireotide s.c. (additionally by country)
- Deaths
- AEs leading to study drug discontinuation, regardless of relationship with pasireotide s.c. (restricted to patients with primary reason for discontinuation documented as AEs or abnormal laboratory values)
- AEs leading to study drug discontinuation, suspected to be related to pasireotide s.c. (restricted to patients with primary reason for discontinuation documented as AEs or abnormal laboratory values)
- AEs requiring dose adjustment or study-drug interruption, regardless of relationship with pasireotide s.c.
- AEs requiring additional therapy, regardless of relationship with pasireotide s.c.
- Adverse events of special interest, regardless of relationship with pasireotide s.c.

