Post-treatment AEs and post-treatment SAEs will be summarized by primary SOC, PT and maximum CTC grade in patients who discontinued pasireotide s.c. prior to completing the 3- year observation period.

In addition, (S)AEs leading to study discontinuation will be listed. Note that there is no respective flag on the eCRF. Therefore the listings will show all (S)AEs which were ongoing at the time of study discontinuation due to AE or which ended the day before.

Also summary on clinically notable AEs (patients who had grade 3/4 AEs, SAEs, AEs leading to discontinuation or other significant AEs) will be prepared for the subgroup of patients from German sites.

Specific groupings of AEs of special interest will be considered and the number of patients with at least one event in each grouping ("category") will be reported. Such groups consist of AEs for which there is a specific clinical interest in connection with pasireotide treatment (i.e. where pasireotide may influence a common mechanism of action responsible for triggering them) or AEs which are similar in nature (although not identical) within project defined group. The specific groupings of AEs as defined in the Attachment 9.2 AESI List (latest documentation available prior to database lock) will be used.

The following tables will be produced:

- AEs of special interest, regardless of relationship with pasireotide s.c., by category, preferred term and maximum CTC grade,
- SAEs of special interest, regardless of relationship with pasireotide s.c., by category, preferred term and maximum CTC grade,
- AEs of special interest, regardless of relationship with pasireotide s.c., by type (any AE, AE suspected to be related to pasireotide s.c., SAE, AE leading to discontinuation, AE requiring dose adjustment or study-drug interruption) and PT

---

Study Code: CSOM230B2410

- AEs of special interest, regardless of relationship with pasireotide s.c., by time interval of onset (0 to < 3 months, 3 to < 6 months, 6 to <9 months, etc.), category and preferred term.

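### Both tables of AEs leading to drug discontinuation are filtered by the patient's primary reason for stopping, so they may omit AEs recorded as having caused the stop

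*SAP*

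**What the plan says.** SAP 8.4.1 lists the selections of treatment-emergent AEs to be tabulated and listed. The two on study drug discontinuation (any relationship; suspected related) each carry the same parenthesis: "restricted to patients with primary reason for discontinuation documented as AEs or abnormal laboratory values". No reason is given. The neighbouring selection, on AEs needing dose adjustment or interruption, has no such condition.

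Protocol 3.5.2.1 says that what was done about each AE goes on the AE CRF. One of its examples is "drug of interest permanently discontinued due to this adverse event". Attribution of the stop is therefore available per event.

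Protocol 3.4.1.1 works per patient: "the investigator should determine the primary reason for a patient's premature withdrawal from this study". The categories offered besides AE include death, withdrawn consent, loss to follow-up and "Unsatisfactory therapeutic effect".

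Two other summaries in SAP 8.4.1 use AEs leading to discontinuation and state no restriction: the table of AEs of special interest (AESIs) by type, and the German-site summary of clinically notable AEs.

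**The concern.** An event-level fact (this AE ended treatment) is made conditional on a patient-level fact (the one primary reason recorded). The two need not agree. A patient may stop because of hyperglycemia together with poor response, or may withdraw consent after an AE that the investigator recorded as ending treatment. There is room for only one primary reason. If it is not AE or abnormal laboratory value, the event is absent from both discontinuation tables.

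The protocol's primary objective is "To document the long-term safety and tolerability profile of pasireotide s.c. when administered as monotherapy or in combination with other therapies". Treatment stopped because of an AE bears directly on tolerability, so a reader of the study report will look at these tables. A rule that can remove AE-caused stops and cannot add any should have a stated reason.

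**Working it through.** The plan has no figure to reproduce. It gives no expected rate of discontinuation due to AEs, and "The sample size for this study is not based on statistical considerations". The check is set logic, followed by an illustration.

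**Step 1: direction.** Define these sets of patients in the safety set:
- U: at least one treatment-emergent AE with the action permanent discontinuation (Protocol 3.5.2.1).
- P: primary reason is AE or abnormal laboratory value (SAP 8.4.1).
- Restricted table: R = U ∩ P.

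R is a subset of U, so its count can never exceed that of U. The two are equal only if no patient in U lies outside P.

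**Step 2: not every lost record is a lost intolerance case.** Protocol 3.5.2.1 also classes some scenarios as AEs when nothing clinical happened; lack of efficacy is one. Split U into C (a clinical event ended treatment) and S (only a special-scenario record did). The understatement of AE-related discontinuation is the part of C outside P. Patients in S outside P are not a loss of tolerability information.

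**Step 3: reconciliation.** Take one patient with hyperglycaemia, which is on the AESI list in SAP Attachment 9.2. The recorded action is permanent discontinuation and the primary reason is consent withdrawal.

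| Output in SAP 8.4.1 | Filter stated? | Patient counted, as worded? |
|---|---|---|
| AEs leading to drug discontinuation, any relationship | yes | no |
| Same, suspected related | yes | no |
| AESIs by type, discontinuation category | no | yes |
| German-site notable AEs (if a German site) | no | yes |
| All AEs | no | yes |

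Read literally, a count for special-interest events could exceed the count for all events.

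**Step 4: illustrative size.** Let N be the number of patients (100 to 200, Protocol 6.7). Let p be the share with a clinical event that ended treatment, and f the share of those whose primary reason is something else. Both p and f are assumptions; the documents give neither.

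Count shown = N × p × (1 − f); count lost = N × p × f.

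With p = 20% (exact Clopper-Pearson 95% intervals):

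| f | N = 100 | N = 200 |
|---|---|---|
| 0 | 20 (20.0%; 12.7 to 29.2) | 40 (20.0%; 14.7 to 26.2) |
| 10% | 18 (18.0%; 11.0 to 26.9) | 36 (18.0%; 12.9 to 24.0) |
| 20% | 16 (16.0%; 9.4 to 24.7) | 32 (16.0%; 11.2 to 21.8) |
| 30% | 14 (14.0%; 7.9 to 22.4) | 28 (14.0%; 9.5 to 19.6) |

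With p and f each from 10 to 30%, the loss runs from 100 × 0.10 × 0.10 = 1 to 100 × 0.30 × 0.30 = 9 patients at N = 100, and from 200 × 0.10 × 0.10 = 2 to 200 × 0.30 × 0.30 = 18 at N = 200. The relative loss equals f. At f = 0 nothing is lost.

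**The case against.** The best defence is that the filter has a use. Because lack of efficacy must be entered on the AE CRF even with no clinical event, a patient who stops for poor response can carry an AE record with a permanent-stop action. Counting every such record would put efficacy failures into a tolerability table, and the primary-reason filter screens them out. This stands, and it shapes the fix. It does not justify the rule as written: the filter acts on the whole patient, so it also removes a genuine adverse reaction recorded as contributing to the same stop.

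A second defence is that the CRF lacks the needed flag. The SAP does say "Note that there is no respective flag on the eCRF", but that sentence concerns AEs leading to study discontinuation, not drug discontinuation.

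A reader might also infer more than the documents support:
- **Interim and final counts are not comparable.** SAP 2.2.1 lists interim tables by title only, and SAP 4.1 says the analysis is the same at every time point. A title that omits the filter does not show that the filter is not applied. The same caution applies to the special-interest and German-site summaries, so the mismatch there is possible, not proven.
- **Abnormal laboratory value is an invalid category.** It is missing from the list in Protocol 3.4.1.1, but that list is for withdrawal from the study. SAP 4.2.1 reports reasons for stopping medication and reasons for leaving the study, and the medication field may have its own list. The SAP simply does not name the field.
- **This is the study's main tolerability measure.** Neither document says so; discontinuation due to AEs is not an endpoint in Protocol 2.1.1 or 2.2.1.

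**Conclusion.** The point holds in a limited form. The restriction can only lower the two discontinuation summaries, the SAP gives no reason for it, and event-level information that avoids it is already collected. AE-related discontinuation may be understated, and related outputs may not reconcile.

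It does not follow that intolerance is in fact undercounted. That requires at least one patient with a clinical AE recorded as ending treatment and another primary reason, and the documents do not show whether there are any. The illustrated loss (2 to 18 of 200 patients, or 1 to 9 of 100) rests wholly on assumed values of p and f. The naming of death, consent withdrawal and unsatisfactory effect as competing reasons assumes that the field used has categories like those in Protocol 3.4.1.1.

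The effect is confined to the two tables and their listings. The primary endpoint is untouched, the events stay in the all-AE, related-AE, SAE and death outputs where they qualify, and patient disposition still shows the reasons for stopping. The change is worth making before the final tables are run.

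**What to change.** In SAP 8.4.1:
1. Define both discontinuation tables by the AE-level action of permanent discontinuation, and delete the two parentheses.
2. Put special-scenario records without a clinical event, such as lack of efficacy, on a separate row and do not count them as intolerance.
3. Keep the count restricted by primary reason as a supportive row.
4. Apply the same rule to the interim, special-interest and German-site outputs, and say so.
5. Name the CRF field that supplies the primary reason.
6. List patients whose AE-level action and primary reason disagree.

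No new data are needed. The cost is a short SAP edit, the extra rows, one listing and some programming. The reported percentage may come out slightly higher.

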#### 6.1.2 Study drug start and end date

Treatment start date for cohort 1: defined as the first date at which a non-zero dose of pasireotide s.c. was administered during the study and recorded on the DAR (e)CRF.

Treatment start date for cohort 2: defined as the first date at which a non-zero dose of pasireotide s.c. was administered prior to study entry and recorded on the CMD (e)CRF.

Treatment end date (same for the 2 cohorts) (The date of last administration of study drug) is defined as the last date at which a non-zero dose of study drug was administered and recorded on the DAR (e)CRF. If the end of the last dosing period with a non-zero dose is missing, the "last known date patient took study drug" (as reported on the completion panel (CMP)) will be used.

Date of first dose after informed consent (IFC): defined as the first date at which a non-zero dose of pasireotide s.c. was administered during the study (i.e. after IFC) and recorded on the DAR (e)CRF.

If treatment with pasireotide s.c. is still ongoing at the time of data cut-off for analysis (i.e. no end date on DAR and CMP (e)CRF), it will be assumed that treatment was ongoing until the last contact date (see Section 6.1.4).

Periods with a specific dose of study medication may have incomplete start and/or end dates (e.g. FEB2015 to MAR2015), however, it is assumed that month and year are always known. If the day is missing in the start date,

- the 15th of the respective month is used for imputation, if not before the end date of the previous period,
- the day after the previous end date is used otherwise.

After imputation of start dates, incomplete end dates are imputed. The unknown end date is set

- to one day before the next start date if the known month and year are equal to month and year of the next start - 1 day
- to the last day of the known month otherwise.

---

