### 6.1.5 Study day

Study days are calculated relative to the date of first dose during the study. The date of first dose defines Day 1. Day -1 is one day before Day 1, Day -2 two days before Day 1, Day 2 one day after Day 1, and so on. That is, there is no Day 0.

More specifically, the study day is calculated as

study day = (date of assessment/event - date of first dose) + 1

if the assessment or event is on or after the date of first dose, and as

study day = (date of assessment/event - date of first dose)

otherwise.

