#### 6.2.4 Confidence intervals for occurrence rates of AEs and SAEs

The occurrences of AE or SAE by preferred term will be modeled to follow approximately a Poisson process with constant intensity  $\theta$ . The rate parameter  $\theta$  will be estimated as  $\lambda=D/T$ , where

- Numerator ( $D_i$ ) = total number of events (AE or SAEs by PT) observed within the cohorts and overall ( $i=1,2,3$  for cohort 1, 2 and overall, respectively). PTs which were reported more than once on the same day (within the same patient) will be counted as one event under the highest severity grade.
- Denominator ( $T_i$ ) = The sum of exposure time  $t$  across all patients in group  $i$  per 100 patient years. For a single patient the exposure time  $t$  is derived as:  $t = (\text{minimum date of (last dose + 28 days, last contact day, analysis cutoff day)} - \text{date of first dose during study} + 1) / 365.25$ . The sum of the exposure time of all patients in group  $i$  will be divided by 100 to obtain the exposure time per 100 patient years.
- Note: the analyses of safety and tolerability assessments will concentrate on the on-treatment period, defined to be the period from Day 1 to 28 days after last dose of pasireotide s.c. i.e. the exposure period for  $T_i$  is accordingly adjusted.

Conditionally on  $T$ , an exact  $100*(1-\alpha)\%$  confidence interval for a Poisson variable with parameter  $\theta*T$  and observed value  $D$  can be obtained based on (Garwood, 1936), from which an exact  $100*(1-\alpha)\%$  confidence interval for  $D/T$  will be derived as follows (Sahai, 1993; Ulm, 1990):

$$\text{Lower confidence limit } L = \frac{0.5c_{\alpha/2,2D}}{T} \quad (\text{in SAS: } (0.5*\text{cinv}(\alpha/2,2*D(i))/T(i))$$

$$\text{Upper confidence limit } U = \frac{0.5c_{1-\alpha/2,2D+2}}{T} \quad (\text{in SAS: } (0.5*\text{cinv}(1-\alpha/2, 2*D(i)+2)/T(i)) \text{ for } i=1,2,3 \text{ and } D(i) > 0 \text{ and } 0 \text{ otherwise,}$$

where  $c_{\alpha,k}$  is the  $\alpha$ th quantile of the Chi-square distribution with  $k$  degrees of freedom.

Garwood, F. 1936. Fiducial limits for the Poisson distribution. *Biometrika*. 28(3/4):437-442

Ulm, K. 1990. A simple method to calculate the confidence interval of a standardized mortality ratio. *American Journal of Epidemiology* 131(2):373-375.

Sahai, H. and Khurshid, A. (1993a). "Confidence intervals for the mean of a Poisson distribution: A review", *BiomtrcJ*, 35, 857-867.

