## 8.4 SAFETY ANALYSIS

Safety and tolerability assessments include AEs, vital signs (blood pressure, heart rate, body temperature), blood glucose (fasting plasma glucose, Hemoglobin A1c), hormones (GH, IGF-1, TSH/free T4), liver enzymes (AST, ALT, alkaline phosphatase,  $\gamma$ GT, total bilirubin), hematology, electrolytes, gallbladder ultrasound and ECGs.

The analyses of safety and tolerability assessments will concentrate on the on-treatment period, defined to be the period from Day 1 to 28 days after last dose of pasireotide s.c. Post-treatment events and assessments (i.e. events and assessments started or performed after the on-treatment period) will be analyzed. In particular, the change between on-treatment period and the period from 28 days after last dose of pasireotide to 90 days after discontinuing pasireotide s.c. treatment will be investigated for continuous parameters in patients who permanently discontinue pasireotide s.c. prior to completing the 3-year observation period.

All safety analyses will be based on the safety set and summarized overall and by cohort. Baseline is described in Section 6.1.6

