### **Occurrences of AEs and SAEs adjusted for exposure**

The exposure times by cohort is different, therefore, exposure adjusted occurrence rates will aid in the interpretation of differences in the occurrence of AEs/SAEs. Exposure adjusted occurrence rates will be presented (per 100 years of patient exposure), together with 95% confidence intervals. Summaries will be presented for treatment emergent AEs and SAEs.

Confidence intervals will be derived assuming a Poisson process for the occurrence of AEs (SAEs). See Section 5.4 for further details.

Summaries of exposure adjusted occurrence rates will be produced for AEs and SAEs by PT. Only AEs (SAEs) with more than 2 occurrences per preferred term will be displayed.

The analyses on occurrences of AEs and SAEs will be repeated by country.

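### The AESI time-of-onset table has no number at risk or person-time and by default times prior users from their first on-study dose, so it can show falling or early risk where there is none

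*SAP*

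**What the plan says.** **The table.** SAP 8.4.1 plans AESIs "by time interval of onset (0 to < 3 months, 3 to < 6 months, 6 to <9 months, etc.), category and preferred term". For AESI groupings, the statistic it describes is "the number of patients with at least one event in each grouping". It gives no time zero, no number at risk and no person-time for the onset intervals.

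**The default rules.** SAP 8.4 bases all safety analyses on the safety set, overall and by cohort, and concentrates on an on-treatment period "defined to be the period from Day 1 to 28 days after last dose of pasireotide s.c". SAP 6.1.5 sets the general clock: "Study days are calculated relative to the date of first dose during the study". For patients who used pasireotide before entry, SAP 6.1.2 also has a second, earlier date: "Treatment start date for cohort 2: defined as the first date at which a non-zero dose of pasireotide s.c. was administered prior to study entry". SAP 8.4.1 does not say which date the onset table uses.

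**Who leaves.** Protocol 3.4.1.1 withdraws patients who permanently stop pasireotide before three years and collects data for three more months.

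**The rates.** SAP 6.2.4 models event counts by preferred term as approximately "a Poisson process with constant intensity". It divides by on-study exposure up to 28 days after the last dose. SAP 8.4.1 states that "exposure adjusted occurrence rates will aid in the interpretation of differences in the occurrence of AEs/SAEs". (It refers to Section 5.4 for the method, which is in 6.2.4.) These rates are not split by interval or AESI category.

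**At-risk rules elsewhere.** The urinary free cortisol response analysis (SAP 8.2.1.1) includes only patients treated during a window and followed to its end. The single/combination therapy summary (SAP 8.3) includes only patients still on drug at the end of each period.

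**The concern.** The primary objective is long-term safety, and readers will use this table to judge whether AESI risk rises, falls or stays level with time on drug. A count of patients per interval cannot answer that when the number observed shrinks. Late counts fall because patients have stopped the drug and, if each patient is counted once, because some have already had their event.

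For Cohort 2, the default clock restarts at the first on-study dose. An event after two years on drug can then fall in the first on-study interval. In Cohort 1 the first on-study dose is the treatment start, so its timing is right. The mis-timing affects the Cohort 2 and overall columns only.

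The exposure-adjusted rates do not fill the gap. They average over the whole on-treatment period, so they cannot show a trend. If risk changes with time on drug, two cohorts with the same risk curve can also have different averages.

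**Working it through.** **Inputs.** The documents give the 3-month intervals (SAP 8.4.1), three years of follow-up (Protocol 3.1) and withdrawal on discontinuation (Protocol 3.4.1.1). They give no discontinuation rate, AESI hazard or Cohort 2 size, so there is no planned figure to reproduce. All rates below are assumptions. The 28-day tail after the last dose is ignored.

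**1. Interval counts under constant risk.** Let λ be the event hazard, μ the discontinuation rate within the interval, and R(a) the proportion still on drug at time a in years. The expected proportion of all patients with a first event in [a, b) is

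R(a) × e^(−λa) × λ/(λ+μ) × [1 − e^(−(λ+μ)(b−a))].

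Take λ = 0.20 per patient-year (PY) with retention of 50% at 12 months and 25% at 36 months. Then μ = ln 2 = 0.693 in year 1 and (ln 2)/2 = 0.347 afterwards.

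- Months 0-3: 0.2/0.893 × (1 − e^(−0.893×0.25)) = 0.2239 × 0.2001 = 4.48%.
- Event-free and on drug at month 33: 0.5 × e^(−0.347×1.75) × e^(−0.20×2.75) = 0.2726 × 0.5769 = 15.7%.
- Months 33-36: 0.157 × 0.2/0.547 × (1 − e^(−0.547×0.25)) = 0.157 × 0.3659 × 0.1277 = 0.74%.
- Total fall: 4.48/0.74 = 6.1-fold. Depletion of first events accounts for e^(0.20×2.75) = 1.73 and dropout for 6.1/1.73 = 3.5.

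| Retention at 12/36 months | Months 0-3 | Months 33-36 | Total fall | From depletion | From dropout |
|---|---|---|---|---|---|
| 100%/100% | 4.88% | 2.81% | 1.7 | 1.7 | none |
| 70%/50% | 4.67% | 1.44% | 3.2 | 1.7 | 1.9 |
| 60%/35% | 4.58% | 1.02% | 4.5 | 1.7 | 2.6 |
| 50%/25% | 4.48% | 0.74% | 6.1 | 1.7 | 3.5 |

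Over a wider range (λ from 0.1 to 0.4 per PY, constant discontinuation of 0.2 to 0.8 per year), the last count is 0.44 down to 0.04 of the first.

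**2. The same data with an at-risk denominator.** Dividing by patients at risk at the start of the interval gives 4.5% in months 0-3 and 0.74/15.7 = 4.7% in months 33-36. Dividing by person-time gives λ, 20 per 100 PY, in every interval and at every retention level.

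**3. Cohort 2 timing.** Suppose an event can occur only after 12 months on drug, at a constant hazard from then on, and Cohort 2 enters with 12 months' prior use. On the on-study clock, the share of Cohort 2 events labelled as before month 12 is (1 − e^(−μ))/(1 − e^(−3μ)):

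- μ = 0.2: 0.181/0.451 = 40%
- μ = 0.5: 0.393/0.777 = 51%
- μ = 0.8: 0.551/0.909 = 61%

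In the overall column the share is 14% to 54% when Cohort 2 makes up 25% to 75% of patients. Timed from treatment start it is 0%.

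**4. Whole-period rates.** Suppose risk is 1.0 per PY in the first 3 months on drug and 0.2 afterwards, and all Cohort 2 patients are past month 3 at entry. Over three years without dropout:

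- Cohort 1: (0.25 × 1.0 + 2.75 × 0.2)/3 = 0.80/3, about 27 per 100 PY.
- Cohort 2: (3 × 0.2)/3, 20 per 100 PY.

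With 50%/25% retention, Cohort 1 contributes 0.230 PY per patient in months 0-3 and 1.443 PY in total. Its rate is (0.230 × 1.0 + 1.213 × 0.2)/1.443, about 33 per 100 PY. Cohort 2 stays at 20.

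**The case against.** Much of the case on the other side stands, and it limits the point.

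- **Clock.** A reader might infer that AESI timing runs from enrolment. SAP 8.4.1 names no origin. The default is the first on-study dose, and an earlier Cohort 2 date is also defined. The origin of this table is therefore inferred from general rules.
- **Dropout.** A reader might put the whole 6-fold fall down to dropout. About 1.7-fold of it comes from counting first events only. SAP 8.4.1 counts a patient once per AE category but does not say whether that applies within or across intervals. If a patient can count in several intervals, roughly the dropout part remains.
- **Rates.** A reader might infer that the constant-intensity rates turn attrition into falling risk. They do not: they divide by exposure and show no time trend at all.
- **Other outputs.** It is tempting to call this the only safety output with a time axis, or the safety set the only denominator. ECG values, pulse, temperature and gallbladder findings are summarised by time window (SAP 8.4.3 to 8.4.5), and SAP 8.4.1 itself uses exposure time for the rates.
- **Cohort contrast.** Stopping at one year without dropout would give 0.25 × 1.0 + 0.75 × 0.2 = 0.40, or 40 versus 20 per 100 PY. The design follows patients for three years, where the figure is 27 versus 20. SAP 4.2.1 also has a prior-use category of three months or less, so not every Cohort 2 patient need be past the early period.
- **Safeguards.** Results are shown by cohort, and prior-use duration and both exposure measures are reported. Subgroups by prior duration are possible, but they are conditional and not tied to this table. The study is exploratory with no hypothesis tests.

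None of this supplies a denominator for the onset intervals or settles the Cohort 2 clock.

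**Conclusion.** The point holds for the onset table. Following the SAP's default rules, its late counts fall under constant risk, and prior users' late events can appear early. The SAP already restricts to treated patients in two other summaries, so the principle is not foreign to it.

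Under the assumed 0.20 per PY, the false decline is about 6-fold at 50%/25% retention and 3.2-fold at 70%/50%. Dropout accounts for 3.5-fold and 1.9-fold of these respectively. The real size cannot be fixed from the documents. The direction does not depend on the exact values: any discontinuation lowers late counts while the person-time rate stays flat.

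The rates in 6.2.4 are a separate and smaller matter. They are valid averages over exposure, but they hide time trends and can differ between cohorts that share one risk curve. For a descriptive study this is a change that should be made. It does not invalidate the primary incidence summary.

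**What to change.** 1. State time zero for the AESI onset table. Time Cohort 2 from its SAP 6.1.2 treatment start date, with delayed entry at the first on-study dose, or present the onset-timing table for Cohort 1 only.
2. For each interval and AESI category, report patients at risk (on treatment or within 28 days of the last dose, with no earlier event in that category), patients with a first event, person-time, and events per 100 PY.
3. Optionally, add AESI-category rates in a few broad periods since treatment start, such as splits at 3, 12 and 24 months. Do this by category, not by preferred term, and as a supplement to the whole-period rates.

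The required dates are already defined in SAP 6.1.2 and 6.2.4, so the cost is programming. With 100 to 200 patients, confidence intervals in late periods will be wide; that reflects how little late follow-up there is. Events before enrolment are not collected, so in Cohort 2 a first event means the first on study, and a footnote should say so.
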